3.2 Schedule of Visits and Assessments

The schedules of visits and assessments are provided below.

Table 3-1. Schedule of Visits and Assessments for the Treatment Period

Treatment Period

Day (D)/Week (W)	Screening	Qual. #1	Qual. #2 (Day 1)	W1 (Day 8±2)	W2 (Day 15±3)	Post Day 1 Treatment	W4 ¹ (Day 29±3)
Visit	1	2	3.0	3.1	3.2	4.0	4.1
Hour (XY = XY:00)	--	09	09	11	16	09	11
Informed Consent	X						
Inclusion/Exclusion	X	X	X	X			
Washout ²	X						
Demography	X						
Medical/Ophthalmic History	X	X	X				
Concomitant Medications	X	X	X	X	X	X	X
HR/BP	X	X	X	X	X	X	X
Urine Pregnancy Test ³	X						X
Clinical Labs (Chem/Hem/UA)	X ⁴						X
Symptoms/AEs ⁵	X	X	X	X	X	X	X
NEI VFQ-25 Questionnaire		X					
BCVA	X	X	X	X	X	X	X
Contrast Sensitivity		X					
TOP	X	X ⁶	X ⁶	X ⁶	X	X	X
Biomicroscopy	X	X	X	X	X	X	X
Gonioscopy ⁷ / Pachymetry ⁸	G/P						
Visual Field ⁹	X						
Ophthalmoscopy (dilated)	X						X
Eye-Drop Instillation Evaluation	X						
Study Medications Dispensed				X			
Study Medications Collected					X ¹⁰		X
Study Completed							X

Abbreviations: HR/BP = heart rate/blood pressure; Chem/Hem/UA = Chemistry/Hematology/Urinalysis; AE = adverse event; IOP = Intraocular pressure.
Early Discontinuation: Visit 6.0 procedures are to be completed plus a dilated ophthalmoscopy examination.
Visit Requirements: + IOP measurements will be 09:00 (+30 mins), 11:00 (+30 mins) and 16:00 (± 30 mins) hours with the exception of the Visit 1 (Screening).

1. If subjects develop cornea verticillata at visit 4 or visit 5, study procedures for visit 6 (Exit Visit) will be completed before entering into the observational period.
2. Subjects currently using ocular hypotensive medications must undergo a minimum washout period (see Section 5.7.1).
3. Urine pregnancy test for women of childbearing potential is required.
4. For subjects who are unable or unwilling to have blood drawn and urine collected for clinical labs at Visit 1 (Screening), the blood and urine sample may be drawn at Visit 2 (Qualification Visit #1) so long as the results of the clinical labs are available for that subject prior to Visit 3 (Qualification Visit #2).
5. Ocular symptoms: Subjects will be queried at each visit "How are you feeling?" and treatment emergent AEs beginning at Visit 4 will be documented on the AE form. Additional symptoms reported after screening and before randomization will be documented on the medical history form. Adverse events will be recorded for every study visit (i.e., at 09:00, 11:00, and 16:00 hours) as needed.
6. Individuals returning at an Unscheduled Visit within 1 week to re-attempt IOP qualification are required to only re-measure IOP in both eyes.
7. Gonioscopy evaluation up to 3 months prior to randomization is acceptable.
8. Pachymetry within 1 week prior to screening is acceptable.
9. Entry visual field evaluation up to 3 months prior to randomization is acceptable. Visual field collection must meet the requirement for automated threshold visual field assessment (e.g., 30-2 or 24-2 Humphrey) and reliability.
10. Collect kit(s) dispensed during the Day 1 visit.

Table 3-2. Schedule of Visits and Assessments for the Observational Period

Observational Period		OBS Visit 1 (Day 1)		OBS Visits 2-4 Monthly Visit x3 (30 ± 5 days if Cornea Verticillata Persist)		OBS Visit 5 and up Bi-monthly Visits after 3rd Monthly visit (60 ± 5 days if Cornea Verticillata Persist)		Final Visit if Resolution/ Stabilization of Cornea Verticillata 1,2 is confirmed	
Study Procedures	Visit when cornea verticillata is diagnosed								
Discontinuation of IP	X								
Commed Review	X		X		X		X		
Symptoms/ Assessment of Ocular and General Health	X		X		X		X		
VFQ-25	X		X		X		X		
Best Corrected Visual Acuity	X		X		X		X		
Contrast Sensitivity	X		X		X		X		
Cornea Verticillata Grading	X		X		X		X		

¹ Should have a grading score of zero OU or stabilization confirmed to exit the study.

² If cornea verticillata grading is zero at any visit, or stabilization of cornea verticillata is confirmed, the subject completes outlined procedures listed in Final Visit and exits the study.

4. Study Treatments

Subjects will be randomized to receive netarsudil ophthalmic solution (0.01%, 0.02%, or 0.04%) or its placebo, administered OU. Subjects will instill one drop into each eye QD in the evening between 20:00 and 22:00 hours. Study drug doses will be administered by the study subjects. For subjects deemed unable to self-administer the doses, a guardian or alternative caregiver will be asked to administer the medication. All subjects will administer study treatment for approximately 28 days.

4.1 Method of Assigning Subjects to Treatment Groups

A randomization code for allocating the treatments will be prepared by an independent biostatistician who is not involved in the day-to-day conduct of the study. Subjects will be randomized using IWRs in a 1:1:1:1 ratio to receive netarsudil ophthalmic solution (0.01%, 0.02% or 0.04%) or its placebo and will be stratified by site.

4.2 Masking

Treatment assignments will be masked to the Investigator, the clinical study team (Sponsor, personnel involved in day to day study management, Monitors, Data Managers, and Statisticians), and the subjects for the duration of the study. Only in case of medical emergency or occurrence of AEs that warrant unmasking in the opinion of the Investigator, will the treatment assignment(s) be unmasked and made available to the Investigator and the Sponsor Medical Monitor or designee. Individual unmasking by the Investigator will normally result in withdrawal of the subject from the study and should only be performed for the specific subject requiring unmasking. In the absence of medical need, the randomization code will not be available to the above personnel until after the study is completed and the database is unlocked.

5. Sample Size and Power Considerations

Assuming a two-sided test with alpha = 0.05, a common standard deviation (SD) of 3.5 mmHg at each time point yielding a common SD of 3.0 for the diurnal mean, and a correlation among time points of 0.60, 49 intent-to-treat (ITT) subjects per arm yields at least 90% power to demonstrate superiority of netarsudil (0.01%, 0.02%, or 0.04%) to placebo in mean diurnal study eye IOP (average of 09:00, 11:00, and 16:00 hours) at the Week 4 visit assuming a difference of at least 2.0 mmHg in the mean diurnal IOP. Accounting for approximately a 5% discontinuation rate, 52 subjects per arm (208 total) will be enrolled.

6. Data Preparation

Study data will be recorded via electronic case report forms (eCRF). Each authorized study staff member will receive a unique access account in order to use the Electronic Data Capture (EDC) system. Access accounts will not be shared among study staff. Authorized users will make entries and/or changes to the eCRFs via a secure internet access. Each completed set of eCRFs will be reviewed by the Investigator

who will then electronically sign and date the eCRF confirming that data for the subjects are complete and accurate.

Final analyses outlined in this document will be carried out after the following have occurred:

- All data management requirements are met according to [REDACTED] standard operating procedures, including data entry, performance of edit and validation checks, documentation and resolution of data queries, and database lock with written authorization provided by appropriate [REDACTED] and Sponsor personnel.
- Protocol deviations have been identified and status defined (major/minor deviations).
- Analysis populations have been determined.
- Randomized treatment codes have been unmasked.

7. Analysis Populations

7.1 Intent-to-Treat Population

The ITT population will include all randomized subjects who have received at least one dose of study drug. This population will be the primary population for efficacy analyses and will be used to summarize all efficacy variables and will summarize subjects as randomized.

7.2 Per Protocol Population

The per protocol (PP) population is a subset of the ITT population, which will include those subjects who do not have major protocol deviations likely to seriously affect the primary outcome of the study as judged by a masked evaluation prior to the unmasking of the study treatment. This population will be the secondary population for efficacy analyses and will be used to summarize a subset of efficacy variables. If the PP and ITT populations are exactly the same, then additional efficacy analyses on the PP population will not be performed. The PP population will summarize subjects as treated.

7.3 Safety Population

The safety population will include all randomized subjects who have received at least one dose of study drug. This population will be used to summarize safety variables and will summarize subjects as treated.

7.4 Cornea Verticillata Safety Population

The cornea verticillata safety population will include all subjects in the safety population who develop cornea verticillata during the study. This population will be used to summarize safety variables within the observational period and will summarize subjects as treated.

8. General Statistical Considerations

8.1 Unit of Analysis

The unit of analysis for efficacy will be the study eye. If the subject qualifies in only one eye, then this eye is designated the study eye. If the subject qualifies in both eyes, then the study eye will be the eye

with the higher IOP at 09:00 hours on Visit 3.0. If both eyes have the same IOP at 09:00 hours on Visit 3.0, then the right eye will be the study eye.

8.2 Missing or Inconclusive Data Handling

Any missing, unused, or spurious data will be noted in the final CSR. Analyses will be performed primarily on the ITT population with multiple imputation techniques (e.g., Monte Carlo Markov Chain [MCMC]) used to impute missing data, and secondarily using observed data only and last observation carried forward (LOCF) where LOCF will be performed using time-relevant measures (i.e., from the same time point of the most recent visit with a non-missing value). The analyses will also be repeated on the PP population to determine the robustness of results.

8.3 Definition of Baseline

For diurnally-adjusted IOP, baseline will refer to the time-relevant measure at Visit 3 (e.g., IOP at 09:00 hours at Visit 3.0 will be the baseline for 09:00 hours at Visit 4.0, Visit 5.0 and Visit 6.0; etc.). For all other variables, baseline is defined as the last measurement prior to the first dose of study drug. An additional definition of baseline for conjunctival hyperemia will also be used: baseline (pre-washout) will be defined as the conjunctival hyperemia measure at Visit 1. Change from baseline will be calculated as: Follow-up Visit – Baseline Visit.

8.4 Data Analysis Conventions

All data analysis will be performed by [REDACTED] Statistical programming and analyses will be performed using SAS® Version 9.4 or higher. Output will be provided in rich text format (RTF) for tables and portable document format (PDF) for tables, listings, and figures using landscape orientation. All study data will be listed by subject, treatment, and visit / time point (as applicable) based on all randomized subjects unless otherwise specified.

Summaries for continuous and ordinal variables will include the number of observations (n), arithmetic mean, SD, median, minimum, and maximum. Minima and maxima will be reported with the same precision as the raw values; means and medians will be presented to one additional decimal place than reported in the raw values. Standard deviations will be presented to two additional decimal places than reported in the raw values. Summaries for discrete variables will include frequency counts and percentages. All percentages will be rounded to one decimal place (i.e., XX.X%).

All statistical tests will be two-sided with a significance level of 0.05 ($\alpha = 0.05$) unless otherwise specified. Confidence intervals (CIs) for differences between treatment groups will be two-sided at 95% confidence. All p-values will be rounded to four decimal places; p-values less than 0.0001 will be presented as "<0.0001"; p-values greater than 0.9999 will be presented as ">0.9999."

Unless otherwise specified, summaries will be presented by treatment group and, where appropriate, visit / time point.

8.5 Assessment Time Windows

In general, it is intended that all safety and efficacy data (with some exceptions) will be summarized at each time point collected regardless of assessment time windows. Because subjects may have an early termination visit at any time or may have unscheduled visits, the following conventions will be implemented.

For all safety and efficacy data, unscheduled visits are not included in the analyses unless they are considered as baseline.

The assessment visit date or start date (e.g., AEs) will be used to calculate study day, defined as the number of days from the day of first dose (Visit 3). The day of first dose (Visit 3) is considered study day 1, so study day will be computed as: (Date of Assessment Data – Date of Visit 3) + 1.

In all by-visit safety assessments, end of study visits and early termination visits will be combined in order to present all data available for each subject; early termination visits will not be windowed into the nearest fitting study visit. Each subject will have one end of study visit.

For efficacy outcomes, early termination data will not be combined with end of study visit information as the timing of the outcome measure is integral to the analysis. Instead, the efficacy outcome will be windowed into the nearest study visit, where Visit 4 has a \pm 2 day window, and Visit 5 and Visit 6 have a \pm 3 day window.

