7.5 Unscheduled Visits

An unscheduled visit may be any visit to the Investigator other than the specific visits requested in the protocol as possibly required for the subject's ophthalmic condition.

The Investigator will perform all procedures necessary to evaluate the study participant at these visits and record any AEs in the CRF.

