15.1 Adverse Events

An AE is defined as any untoward medical occurrence associated with the use of a drug in humans, whether or not the event is considered drug-related. All AEs occurring during the study, regardless of the assumption of causal relationship, must be documented on the respective CRF. AEs should be

documented from the time the subject receives the first dose of study drug until 30 days after the last dose of study drug.

Treatment-emergent adverse events (TEAEs) are defined as any event that occurs or worsens on or after the day that randomized study treatment is initiated, and by study completion date.

Adverse events are coded using the MedDRA/J, Version 21.1. An overall summary will be presented to report the number of events and incidents of subjects having at least one event in the following categories:

- TEAEs
- Ocular TEAEs
- Non-ocular TEAEs
- Serious TEAEs
- Treatment-related TEAEs (reported as possibly related or related to the study drug)
- Treatment-related serious TEAEs
- TEAEs by maximum severity
- TEAEs leading to study drug discontinuation
- TEAEs resulting in death

Separate summaries will be provided for the number and percentage of TEAEs by SOC and PT for the following categories as well as the p-values for comparing the incidence between each netarsudil (0.01%, 0.02%, and 0.04%) group and placebo:

- Ocular TEAEs
- Non-ocular TEAEs
- Serious TEAEs
- Treatment-related TEAEs (reported as possibly related or related to the study drug)

If a subject reports the same PT multiple times within the same SOC, that PT will only be reported once within that SOC. As with the PT, if a subject reports multiple conditions within the same SOC, that SOC will only be reported once. In the summary, SOC will be listed in ascending alphabetical order; PTs will be listed in order of descending frequency within each SOC.

Treatment-emergent AEs will also be summarized by SOC, PT, and maximum severity. If a subject experiences more than one AE within SOC or PT, that subject will be counted only once for that event under the maximum severity.

All AEs will be presented in a subject listing. In addition, all serious AEs and AEs leading to study drug discontinuation will be listed separately.

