15.3 Biomicroscopy Examination

Biomicroscopy examination of the lids, conjunctiva, cornea, anterior chamber, lens, and iris/pupil will be performed for both eyes of subjects at every study visit.

The results will be summarized using counts and percentages for each treatment group at each visit for study eye and fellow eye separately. Percentages will be based on the number of subjects in each treatment group with non-missing values.

A summary table of the number and percentage of subjects with at least one severity grade increase from baseline will be presented by region, finding, visit, and eye (study eye and fellow eye). Another summary table will be presented for the number and percentage of subjects with biomicroscopy finding judged to be clinically significant by the Investigator by region, finding, visit time point, and eye (study eye and fellow eye). Fisher's exact tests will be used to compare incidence between treatment groups in both tables. Note: iris/pupil will not be analyzed in the table.

Additionally, Conjunctival hyperemia will also be summarized using continuous summary statistics including change from baseline and change from Visit 1. Two-sample t-tests as well as Wilcoxon rank sum tests will be used to test the difference between treatment groups.

A subject listing of the biomicroscopy parameter results will be produced. A separate listing will be generated for subjects with a criterion change, defined as a +1 unit increase from baseline.

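### SAP 8.5 keeps unscheduled post-dose visits out of the biomicroscopy incidence tables, and no any-post-baseline summary recovers the findings made there

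*SAP*

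**What the plan says.** SAP 8.5 (Assessment Time Windows) sets the rule: "For all safety and efficacy data, unscheduled visits are not included in the analyses unless they are considered as baseline". Use as baseline is the only exception. A later rule in the same section is confined to by-visit safety assessments, where "end of study visits and early termination visits will be combined in order to present all data available for each subject". The rule on unscheduled visits has no such limit.

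Protocol 7.5 treats any visit outside the specified ones as unscheduled and says: "The Investigator will perform all procedures necessary to evaluate the study participant at these visits and record any AEs in the CRF".

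SAP 15.3 plans two biomicroscopy incidence tables. One gives "the number and percentage of subjects with at least one severity grade increase from baseline". The other counts subjects whose findings the investigator judged clinically significant. Both are broken down by visit and by eye, and both carry Fisher's exact tests between treatment groups. The table list in SAP 21 numbers them 14.3.3.6 and 14.3.3.7. It also has Table 14.3.3.5, on clinically significant increases in conjunctival hyperemia, whose layout SAP 15.3 does not describe. No worst-on-treatment or any-post-baseline summary is described anywhere.

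Two other provisions matter. SAP 15.1 defines a treatment-emergent adverse event by date: "any event that occurs or worsens on or after the day that randomized study treatment is initiated, and by study completion date". SAP 8.4 covers listings: "All study data will be listed by subject, treatment, and visit / time point (as applicable) based on all randomized subjects unless otherwise specified".

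**The concern.** Protocol 7.5 links unscheduled visits to the possible needs of the subject's eye condition. Some will follow a complaint, and a short-lived slit-lamp finding may be seen only then. Leaving such visits out of by-visit means is sensible, because they belong to no nominal visit. Leaving them out of every incidence count is harder to defend, because the question there is whether the subject ever had the finding on treatment.

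Ocular safety relative to placebo is part of the primary objectives, and the study title names the optimum concentration as a purpose. The biomicroscopy incidence tables are where graded corneal and conjunctival findings are compared between concentrations and placebo. As written, they can omit subjects whose finding was graded and recorded.

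**Working it through.** **1. Follow one finding through the outputs.** Suppose a one-grade rise is seen at an unscheduled slit-lamp examination on Day 21 and has gone by Day 29.

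| Output | Basis | Does it appear? |
|---|---|---|
| Tables 14.3.3.6 and 14.3.3.7, with Fisher tests | SAP 8.5, 15.3 | No |
| Table 14.3.3.5 (hyperemia) | SAP 8.5, 21 | No |
| Ocular adverse-event tables 14.3.1.2 and 14.3.1.6 | SAP 15.1, dated by onset or worsening | Only if recorded as an adverse event |
| By-visit safety tables, if the visit was the subject's early termination | SAP 8.5 | Yes |
| Biomicroscopy listings 16.2.9.1 and 16.2.9.2 | SAP 8.4, 15.3 | Yes, on the ordinary reading, but with no rate |

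SAP 8.5 does not say outright that adverse-event tables and listings are outside the exclusion. That follows only from reading it with SAP 8.4 and 15.1.

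**2. Can the adverse-event tables stand in?** Only in part, because the criteria differ.

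- Protocol 6.8.2 makes conjunctival redness an adverse event when it has risen from Visit 1 and is clinically meaningful.
- SAP 15.3, with the baseline of SAP 8.3, counts a rise of one grade or more over the last pre-dose measurement.
- Protocol 6.8.4 grades adverse-event severity by discomfort and daily activity, not by slit-lamp grade.

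A finding can meet one definition and miss the other.

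**3. Room for a finding to be missed.** Protocol Appendix 1 schedules post-dose biomicroscopy on Days 8, 15 and 29, at three times each: 3 × 3 = 9 examinations. The nominal gaps are 8 − 1 = 7, 15 − 8 = 7 and 29 − 15 = 14 days. A finding must arise and clear within one gap to be seen only at an unscheduled visit.

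**4. Size.** The plan gives no figure for this. The arm size is its own and reproduces: 49 / (1 − 0.05) = 51.6, rounded up to 52, and 4 × 52 = 208. Let *u* be the share of an arm with a finding seen only at an unscheduled visit. This is an assumption, with the range shown. The expected number missing is 52 × *u*:

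- *u* = 1%: 0.5 subjects
- *u* = 2%: 1.0
- *u* = 5%: 2.6
- *u* = 10%: 5.2

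To gauge what that could do to a Fisher test, take a finding not otherwise seen, in *x* of 52 on one arm and 0 of 52 on placebo. The two-sided p-value is 2 × C(52, *x*) / C(104, *x*):

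- *x* = 3: 2 × 22,100 / 182,104 = 0.243
- *x* = 5: 2 × 2,598,960 / 91,962,520 = 0.057
- *x* = 6: 2 × 20,358,520 / 1,517,381,580 = 0.027

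Six missing subjects, all on one arm, would be needed to cross 0.05 by themselves. That exceeds the expected number even at *u* = 10%. Fewer could matter if added to subjects already counted at scheduled visits, but the documents do not allow that to be computed.

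**The case against.** The case against has four parts.

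- **The tables are by visit.** SAP 15.3 lays out both incidence tables by visit, so an unscheduled visit has no column and the visit-specific rates are not distorted. This stands. It does not supply a rate across the treatment period, which the SAP lacks.
- **Rates exist elsewhere.** Ocular adverse events are tabulated with p-values against placebo whatever the visit type. Early-termination visits are kept. Cornea verticillata detected at any visit between Visits 4 and 6 leads to the Visit 6 procedures and grading (Protocol 7.4.1). This stands in part: step 2 shows why adverse-event counts do not replace graded findings.
- **Unscheduled visits need not be symptom-driven.** The protocol also uses the term for repeat pressure qualification before randomization (Protocol 7.2 to 7.3.3), which the baseline exception fits. This stands, but SAP 8.5 is not confined to those visits.
- **Adding the visits has its own bias.** Subjects with more unscheduled visits are examined more often, which can raise incidence on their arm. This stands as a real downside, and is the reason to keep the scheduled-visit results alongside.

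Three stronger readings are tempting and are not supported:

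- A reader might infer that all safety data from unscheduled visits are discarded. The baseline exception, the date-based adverse-event definition, the retained early-termination data and the listings say otherwise.
- A reader might infer that active-minus-placebo incidence is biased toward zero by a known amount. If 4% to 10% of an active arm attended and half had a transient rise, 0.5 × 4% = 2 and 0.5 × 10% = 5 percentage points would be lost, but neither input is in the documents. The 53% conjunctival hyperemia rate in Protocol 1.3 makes more visits on active drug plausible, but it is not a visit rate.
- A reader might infer that an acuity-loss incidence table is affected. SAP 15.2 plans only continuous summaries of acuity. The proportion losing 15 letters is in Protocol 9.7.2 and not in SAP 15.2. That difference is a separate point.

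**Conclusion.** The point holds for biomicroscopy and is minor. Read as written, SAP 8.5 removes unscheduled post-dose findings from the biomicroscopy incidence tables and their Fisher tests, and no other planned summary restores a rate for them. This follows from the text and needs no assumption about frequency.

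The size and direction of any effect are unknown. The illustrative range of about 0.5 to 5.2 subjects per 52-subject arm rests wholly on the assumed 1% to 10%. Nine scheduled slit-lamp examinations in four weeks limit what can be missed, and adverse-event tables and listings capture part of the rest. The pressure analyses use scheduled time points, so the primary efficacy result does not depend on this. The change is worth making because the data are already collected and ocular safety is part of the primary objectives.

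**What to change.** Make three changes to the SAP.

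1. In 8.5, limit the exclusion of unscheduled visits to by-visit summaries and efficacy analyses.
2. In the same place, state that adverse-event tables and all listings include data from unscheduled visits.
3. In 15.3 and in Tables 14.3.3.5 to 14.3.3.7, add an incidence at any post-baseline visit, including unscheduled visits, for each finding and each eye. Keep the scheduled-visit results beside it.

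No acuity row should be added under this point, since SAP 15.2 has no 15-letter summary to extend.

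The cost is a sentence or two and some extra rows, more than one per table because the tables run by finding and eye. No new data are needed. Because an arm with more unscheduled visits is examined more often, the added incidence should be read next to the scheduled-visit figure and not in place of it. The revision history in SAP 20 describes some analyses as already conducted, so rows added after unmasking should be labelled post hoc.
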